9.3.22 CORNEAL AND CONJUNCTIVAL STAINING AT EACH VISIT

Corneal and conjunctival staining scores (0 to 5 scale) at each visit will be summarized by frequency of each score and shift from baseline. Changes from baseline will be analyzed at each time point using Cochran-Mantel-Haenszel (CMH) statistics as described in section 9.3.21.

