### 6.4.1 RESCUE MEDICINE

In the event that rescue medication is required for clinically relevant worsening of keratitis, patients will be provided a concomitant regimen the investigator/treating clinician can initiate:

- Flarex® 0.1% dosed four times a day for up to 10 days as recommended by the prescribing physician.

and

- Instillation of Hylo-Forte® in each eye 5 minutes prior to applying the study ointment. This can be maintained for the duration of the study as recommended by the prescribing physician.

Patients responding to treatment may remain in the study. Patients not-responding to treatment and who are still demonstrating clinically significant keratitis may be temporally discontinued from treatment or discontinued from the study at the investigator/treating clinician's discretion.

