### 8.3.1 DEFINITION OF ADVERSE EVENTS (AE)

An AE is defined as any untoward medical occurrence in a clinical study subject administered a medicinal product which does not necessarily have a causal relationship with this treatment. An AE can therefore be any unfavorable and unintended sign (including an abnormal laboratory finding), symptom, or disease temporally associated with the use of a medicinal (investigational) product, whether or not it is related to the medicinal (investigational) product. This includes an exacerbation of pre-existing conditions or events, intercurrent illnesses, drug interaction or the significant worsening of the indication under investigation that is not recorded elsewhere in the CRF under specific efficacy assessments. Anticipated fluctuations of pre-existing conditions, including the disease under study that do not represent a clinically significant exacerbation or worsening need not be considered AEs.

It is the responsibility of the investigator to document all AEs that occur during the study. AEs will be elicited by asking the subject a nonleading question, for example, "Have you experienced any new or changed symptoms since we last asked/since your last visit?". AEs should be reported on the appropriate page of the CRF.

Some illustrate examples follow to help understand the difference between events meeting the definition of an AE and those that don't.

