7 GENERAL ISSUES FOR STATISTICAL ANALYSIS

Descriptive statistics for continuous variables will include the sample size, mean, standard deviation (SD), median, minimum, and maximum. Percent and frequencies will be provided for categorical variables. Results will be generated by treatment group.

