9.3.3 PROPORTION OF PATIENTS WITH MGS SCORE > 12 AT EACH VISIT

The proportion of patients with an MGS score > 12 at each visit will be summarized using shift tables displaying the frequency and percent of patients in each category (yes/no) by treatment group.

Logistic regression will be performed to compare treatments with respect to the proportion of patients achieving MGS score >12 at each visit, adjusting for baseline MGS score stratum and duration of disease stratum. The odds ratio, along with the 95% CI, for the treatment effect will be presented. Pearson's chi-square test, or Fisher's exact test (if the expected cell count is less than 5 in 25% or more of the cells), will also be performed.

The following pseudocode will be used:

```

PROC LOGISTIC data=xxx;
BY visit;
CLASS treatment (ref = 'AZR-MD-001 VEHICLE') duration baseMGS;
MODEL response =treatment base duration baseMGS;
LSMEANS treatment;
run;

PROC FREQ data=xxx;
BY visit;
TABLE treatment * response/EXACT;
ODS OUTPUT CHISQ = outc (where=(STATISTIC='Chi-Square'))
FISHERSEXACT=outf (where=(NAME1='XP2_FISH'));
Run;

```

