9.3.21 EYELID MARGIN ERYTHEMA AND TELANGIECTASIAS

Eyelid margin erythema and telangiectasias scores at day 14, month 1, month 1.5, and month 3 will be summarized using N, mean, standard deviation, median, minimum, and maximum. Actual values and shifts from baseline will be summarized by parameter and time point. Changes from baseline will be analyzed at each time point using Cochran-Mantel-Haenszel (CMH) statistics to test for a treatment effect.

The following pseudocode will be used:

```
PROC FREQ data=xxx;
BY visit;
TABLE treatment * base * result / CMH;
ODS output CMH=outcmh (where=(ALTHYPOTHESIS='General Association'));
run;
```

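### The SAP's CMH code for staining and lid margin signs makes treatment the stratum, so its p-value does not compare the arms

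*SAP*

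**What the plan says.** SAP 9.3.22 plans frequencies and shifts from baseline for staining graded 0 to 5. It defines the test only by cross-reference: "Changes from baseline will be analyzed at each time point using Cochran-Mantel-Haenszel (CMH) statistics as described in section 9.3.21".

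SAP 9.3.21, on eyelid margin erythema and telangiectasias, states the aim as "using Cochran-Mantel-Haenszel (CMH) statistics to test for a treatment effect". It then gives pseudocode that it says will be used. The table request is "TABLE treatment * base * result / CMH", and the output filter "ODS output CMH=outcmh (where=(ALTHYPOTHESIS='General Association" keeps only the General Association line.

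For contrast, the two-way table in SAP 9.3.3 has treatment as one of the two tested variables: "TABLE treatment * response/EXACT".

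The protocol lists staining and lid margin signs as secondary measures (8.1.2). Section 9.4.3 assigns secondary variables an ANCOVA with treatment as factor. Section 9.4.1 names the Wilcoxon rank-sum test for ordinal variables, and the synopsis names CMH or Wilcoxon. All of these are between-treatment comparisons. SAP 13 lists one change from the protocol, the removal of the pairwise-comparison wording, and does not mention the method for these endpoints.

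**The concern.** The prose and the code in SAP 9.3.21 ask different questions. The prose asks whether the arms differ. The code asks whether a patient's baseline grade predicts the grade at the visit, after adjusting for arm. A programmer who follows the code will produce a p-value that the report labels a treatment effect but that is not one.

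Staining grades would be expected to track within patient. The coded p-value will then tend to be small whether or not the drug does anything. The error would be repeated at each post-baseline visit for corneal staining, conjunctival staining, lid margin erythema and telangiectasias.

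**Working it through.** **How the request is read.** In PROC FREQ, `A * B * C / CMH` takes A as the stratum, B as rows and C as columns, and tests rows against columns within strata.

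- As coded: stratum = treatment, rows = baseline grade, columns = visit grade.
- As the prose intends: stratum = baseline grade, rows = treatment, columns = visit grade.

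The coded statistic sums over arms, so exchanging the arm labels cannot change it.

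**Inputs.** About 30 patients (SAP 4) randomized 1:1 (protocol 4.1) are taken as 15 per arm. The documents give no distribution of staining grades, so the grades below are assumptions. Baseline grades are limited to 0, 1 and 2; protocol 5.2 excludes corneal staining of 3 or more. The SAP states no result for this test, so there is no planned figure to reproduce.

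**Formula.** In one stratum of size n, the General Association statistic is (n − 1)/n times the Pearson X². When k strata have identical tables, Q is k times that value.

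**Example A: identical arms.** Each arm has five patients at each baseline grade. Visit grades 0/1/2/3 have counts 4/1/0/0 from baseline 0, 1/3/1/0 from baseline 1, and 0/1/3/1 from baseline 2.

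- As coded, per arm: column totals are 5, 5, 4, 1, so the expected counts in each row are 5/3, 5/3, 4/3, 1/3. X² by column = 5.2 + 1.6 + 3.5 + 2.0 = 12.3. Then 14/15 × 12.3 = 11.48, and over two identical arms Q = 22.96 on (3 − 1)(4 − 1) = 6 df, p = 0.0008.
- Reordered: at each baseline grade the two arms have the same counts, so Q = 0 and p = 1.0.

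**Example B: active two grades worse.** In every baseline group, vehicle ends at 0,0,0,1,1 and active at 2,2,2,3,3.

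- As coded: within an arm every baseline grade has the same visit counts, so Q = 0 and p = 1.0.
- Reordered, per baseline group (n = 10): the arms are fully separated, so X² = 10. Then 9/10 × 10 = 9, and over three groups Q = 27.0 on 3 df, p = 0.000006.

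**How often the coded test gives p < 0.05.** Assumptions: 15 per arm; baseline 0/1/2 equally likely; visit grade kept within 0 to 5. Close tracking means a change of −1/0/+1 with probability .25/.5/.25. Loose tracking means −2 to +2 with probability .1/.2/.4/.2/.1.

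| Link of visit grade to baseline | Arms identical | Active +1 grade | Active +2 grades |
|---|---|---|---|
| Close tracking | 97% | 94% | 85% |
| Loose tracking | 58% | 48% | 46% |
| Unrelated | 4.1% | 3.2% | 2.8% |

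Down each column the rate changes greatly with tracking. Along each row it does not rise with the treatment effect. One reason for the slight fall is that shifting one arm adds visit-grade columns. With close tracking the visit grades run to 3, 4 or 5, so df goes from 6 to (3 − 1)(5 − 1) = 8 to (3 − 1)(6 − 1) = 10, while the association within each arm gains little or nothing.

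The reordered General Association test with identical arms gives 3.4%, 2.6% and 4.6% down the three rows. With active one grade worse it gives 65.5% under close tracking and 80.4% when the grades are unrelated. With active two grades worse and unrelated grades it gives 99.9%. Under close tracking and one grade worse, the row-mean-scores statistic gives 93.3%, against 65.5% for General Association.

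**A second model.** With normally distributed latent severity, three baseline grades, four visit grades and baseline-visit correlations of 0, 0.5, 0.7 and 0.85, the coded rates with no effect are 3%, 28%, 68% and 95%. With active shifted 1.5 SD lower they are 3%, 19%, 48% and 80%. The reordered test gives about 3% with no effect and 71% to 95% with the shift.

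**The case against.** The strongest reply is that the block is labelled pseudocode, the sentence above it states the right aim, and a careful programmer would notice. The outcome is also one of 22 other efficacy measures (SAP 3.2.2), which SAP 7.5 leaves unadjusted as descriptive. Frequencies and shifts are shown by arm (SAP 7: "Results will be generated by treatment group"), so a tiny p-value beside matching tables would look odd. All of this stands, and it lowers the severity. It does not remove the error: the SAP says this code will be used, and calling a comparison descriptive does not make a test of another hypothesis acceptable.

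Three stronger readings are tempting, and the documents do not support them.

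- *No between-arm test of staining is planned anywhere.* This holds for the SAP only. Protocol 9.4.3 and 9.4.1 both give between-arm tests that cover staining.
- *The error endangers patients.* Protocol 6.4.1 does provide treatment ("In the event that rescue medication is required for clinically relevant worsening of keratitis"), but the treating clinician starts it for an individual, while the final analyses come after the last month 3 visit (SAP 5.2). The AE definition does set apart "significant worsening of the indication under investigation that is not recorded elsewhere in the CRF under specific efficacy assessments", but protocol 8.3.1 also counts exacerbations of pre-existing conditions and disease signs more severe than expected. Biomicroscopy has its own by-arm tables (SAP 10.3). That worsening would drop out of the AE tables is conjecture.
- *The coded test would almost always miss harm.* That needs visit grade to be unrelated to baseline, as in Example B. With close tracking the coded test is usually significant, for the wrong reason.

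**Conclusion.** The point holds as a conflict between prose and code in SAP 9.3.21, carried into 9.3.22. The only test in the SAP for staining and lid margin signs does not, as coded, compare the treatments.

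The structural finding rests on how PROC FREQ reads a three-way table and on no assumption about the data. The rejection rates do rest on assumed baseline mixes and transitions. Across those assumptions the coded rate with identical arms runs from about 3% to 97%, depending on tracking, and it does not rise when a treatment effect is added. The practical hazard is an uninformative and usually small p-value reported as a treatment effect.

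Severity is minor. The MGS and OSDI analyses, their hierarchy and the by-arm descriptive tables are untouched.

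**What to change.** In SAP 9.3.21, and so in 9.3.22, write `TABLE base * treatment * result / CMH`. Baseline grade becomes the stratum and treatment is tested against visit grade. This alone cures the defect.

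Preferably, also change the output filter to keep the Row Mean Scores Differ line, because the grades are ordered. This is a gain in power and not part of the correction.

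Add a row to SAP 13 recording that CMH replaces the ANCOVA of protocol 9.4.3, or the Wilcoxon test of 9.4.1, for these endpoints. The entry can note that the protocol synopsis already allows CMH for ordinal variables.

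The cost is one line of code, one output label and one table row, with no new data or visits. Some p-values for staining and lid margin signs that would have looked significant may no longer be.

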10 SAFETY ANALYSES

	TEMPLATE		
	DOCUMENT #:		TMP-191
	REVISION:		2.0
STATISTICAL ANALYSIS PLAN TEMPLATE	CC #:	836	PAGE 22 OF 25

Safety measures will be analyzed using the safety population and shift tables will be presented for change from baseline variables.

10.1 OCULAR COMFORT QUESTIONNAIRE / STUDY MEDICATION TOLERABILITY

Ocular comfort questionnaire measures (drug felt comfortable, drug felt soothing, drug felt moistening/lubricating, drug enhanced clear vision, drug stickiness, drug blur, drug burning/stinging, and drug discomfort), will be summarized by treatment group for screening, baseline (Day 0), Day 14, Month 1, Month 1.5, Month 3. Summary will include N, mean, standard deviation, median, minimum, and maximum response (measured in %) at each visit, as well as change from baseline.

10.2 BEST-CORRECTED VISUAL ACUITY (BCVA)

A summary of raw visual acuity (number of letters read) by eye (study eye and non-study eye), treatment group, and visit will be provided in tables for screening, Baseline (Day 0), Day 14, Month 1, Month 1.5, and Month 3. Summary will include N, mean, standard deviation, median, minimum, and maximum response (measured in %) at each visit, as well as change from baseline.

The proportion of patients with a change from baseline BCVA ≤ 5 and > 5 and a change from baseline ≤ 10 and > 10 at each visit will be summarized by study eye and non-study eye using shift tables displaying the frequency and percent of patients in each category (≤ 5 and > 5 / ≤ 10 and > 10) by treatment group and eye.

10.3 BIOMICROSCOPY

Biomicroscopy will be summarized by treatment group, eye (study eye and non-study eye), and visit for screening, Baseline (Day 0), Day 14, Month 1, Month 1.5, and Month 3 by treatment group. The summary will include frequency and percent of each response. A shift table (shift form baseline) will be provided by treatment.

10.4 OPHTHALMOSCOPY

Ophthalmoscopy results (lens status, cataract, vitreous and fundus) will be summarized by treatment group, eye (study eye and non-study eye), and visit for screening (dilated) and month 3 (not dilated) using a shift table (shift form baseline).

10.5 INTRAOCULAR PRESSURE (IOP)

	TEMPLATE		
	DOCUMENT #:		TMP-191
	REVISION:		2.0
STATISTICAL ANALYSIS PLAN TEMPLATE	CC #:	836	PAGE 23 OF 25

A summary of raw IOP will be provided by treatment group and eye (study eye and non-study eye) at baseline and Month 3. Summary will include N, mean, standard deviation, median, minimum, and maximum response (measured in %) at each visit, as well as change from baseline.

11 ADVERSE EVENTS

All adverse events (AEs) will be coded using the standardized Medical Dictionary for Regulatory Activities (MedDRA) central coding dictionary, version 23.1 or greater.

11.1 ALL ADVERSE EVENTS

Summaries of incidence rates of individual TEAEs by System Organ Class (SOC) and Preferred Term (PT) will be prepared. Because a subject may experience more than one AE, summaries will provide both the number of subjects experiencing at least one event and the number of events within a reporting period. Percentages provided will be the percent of subjects experiencing one or more adverse events. In addition, incidence of TEAEs will be presented by severity (mild, moderate, severe) and by relationship (unrelated, unlikely, possible, probable, very likely/certain) to investigational treatment. Subjects experiencing an event within a given PT and SOC more than once will be counted under the maximum severity/relationship experienced.

A TEAE is any AE that is new in onset or was aggravated in severity or frequency following the application of first study drug, up to 30 days of receiving the last study drug. If the start date of any AE is incomplete or missing, the event will be assumed to be a TEAE, unless the incomplete start date (month and/or year) or the stop date (complete or incomplete) clearly indicates that the event started prior to the study drug.

A listing of all adverse events will include the subject number, AE number, the AE SOC and PT, the severity of AE, whether or not the AE is classified as serious (SAE), the relationship of the AE to the study intervention, the action taken, the outcome, and the adjudication status.

11.2 ADVERSE EVENTS LEADING TO WITHDRAWAL

A summary of incidence rates (frequencies and percentages) of AEs leading to study withdrawal, by SOC will be prepared for the safety population. A data listing of AEs leading to withdrawal will also be provided, displaying details of the event(s) captured on the CRF.

11.3 SERIOUS ADVERSE EVENTS

	TEMPLATE		
	DOCUMENT #:		TMP-191
	REVISION:		2.0
STATISTICAL ANALYSIS PLAN TEMPLATE	CC #:	836	PAGE 24 OF 25

Summaries of incidence rates and relationship to the investigational drug/procedure of individual SAEs by SOC and PT will be prepared. Summaries will provide both the number of subjects and the number of events within a reporting period. Percentages provided will be the percent of subjects experiencing one or more SAEs. A data listing of SAEs will also be provided, displaying details of the event(s) captured on the CRF.

11.4 DRUG OR PROCEDURE RELATED ADVERSE EVENTS

Summaries of incidence rates of drug and procedure related AEs by SOC and PT will be prepared. Related events include those classified as possible, probable, very likely/certain. Events classified as unrelated or unlikely will be considered not related. Summaries will provide both the number of subjects and the number of events within a reporting period. Percentages provided will be the percent of subjects experiencing one or more study intervention related adverse events. Data listings of drug and procedure related AEs will also be provided, displaying details of the event(s) captured on the CRF.

11.5 DEATHS

Should any subjects die during the course of the trial, relevant information will be supplied in a data listing.

12 OTHER PLANNED ANALYSES

12.1 PLANNED SUBGROUP ANALYSES

12.1.1 SEX

Analyses of the primary efficacy sign and symptom will be repeated by gender.

12.1.2 MGD DIAGNOSIS AND MGS SCORE

Patients will be stratified by duration of MGD diagnosis (i.e., < 5 years or ≥ 5 years) and baseline MGS score for the qualified eye (i.e., the eye meeting the inclusion/exclusion criteria). If the eyes have the same MGS score the right eye will be selected as the study eye.

Thus, subgroup analyses of the primary efficacy sign and symptom are planned for the 4 groups defined by the 2 stratification factors:

1. MGD diagnosis < 5 years and MGS score for the qualified eye < 6
2. MGD diagnosis < 5 years and MGS score for the qualified eye ≥ 6 and ≤ 12

	TEMPLATE		
	DOCUMENT #:		TMP-191
	REVISION:		2.0
STATISTICAL ANALYSIS PLAN TEMPLATE	CC #:	836	PAGE 25 OF 25

3. MGD diagnosis \geq 5 years and MGS score for the qualified eye $<$ 6
4. MGD diagnosis \geq 5 years and MGS score for the qualified eye \geq 6 and \leq 12

13 SUMMARY OF CHANGES FROM THE PROTOCOL

The following table provides a list of changes from the protocol to the SAP, and the justification for each change.

Section	Description	Justification
9 Efficacy Analyses	Removed reference to pairwise comparisons between treatment groups.	Throughout the protocol, there is reference to performing pairwise comparisons between treatment groups which is thought to be leftover from the AZ201801 study where there were more than 2 treatment groups. For this study, we will use LSMEANS to compare the two treatment groups, as applicable.

14 REPORTING CONVENTIONS

All reporting will meet the standards of applicable SOPs.
